10.4. Medication Error, Drug Abuse, and Drug Misuse

Medication Error

For the purposes of this clinical study a medication error is an unintended failure or mistake in the treatment process for an IMP or Alexion AxMP that either causes harm to the participant or has the potential to cause harm to the participant.

Any events of medication error, with or without associated AEs, are to be captured and forwarded to Alexion GPS via email or facsimile ([contact] or [name]) using the Alexion Clinical Study Medication Error Report Form.

A medication error is not lack of efficacy of the study intervention, but rather a human or process related failure while the intervention is under control of the study site staff or participant.

Medication error includes situations where an error:

- Occurred
- Was identified and intercepted before the participant received the drug
- Did not occur, but circumstances were recognized that could have led to an error

Examples of events to be reported in clinical studies as medication errors:

- Drug name confusion
- Dispensing error, eg, medication prepared incorrectly, even if it was not actually given to the participant
- Drug not administered as indicated, eg, wrong route or wrong site of administration
- Drug not taken as indicated, eg, tablet dissolved in water when it should be taken as a solid tablet
- Drug not stored as instructed, eg, kept in the refrigerator when it should be at room temperature
- Wrong participant received the medication (excluding Interactive Response Technology [IRT]/Randomization and Trial Supply Management [RTSM] errors)
- Wrong drug administered to participant (excluding IRT/RTSM errors)

Examples of events that do not require reporting as medication errors in clinical studies:

- Errors related to or resulting from IRT/RTSM including those which led to one of the above listed events that would otherwise have been a medication error
- Participant accidentally missed drug dose(s), eg, forgot to take medication
- Accidental overdose (will be captured as an overdose [refer to Section 6.8 for information on treatment of overdose])
- Participant failed to return unused medication or empty packaging

Medication errors are not regarded as AEs but AEs may occur as a consequence of the medication error.

Drug Abuse

For the purpose of this study, drug abuse is defined as the persistent or sporadic intentional, non-therapeutic excessive use of IMP or Alexion AxMP for a perceived reward or desired non-therapeutic effect.

Any events of drug abuse, with or without associated AEs, are to be captured and forwarded to Alexion GPS via email or facsimile ([contact] or [name]) using the Alexion Clinical Study Drug Misuse or Drug Abuse Report Form. This form should be used both if the drug abuse happened in a study participant or if the drug abuse involves a person not enrolled in the study (such as a relative of the study participant).

Examples of drug abuse include but are not limited to:

- The drug is used with the intent of getting a perceived reward (by the study participant or a person not enrolled in the study)
- The drug in the form of a tablet is crushed and injected or snorted with the intent of getting high

Drug Misuse

Drug misuse is the intentional and inappropriate use (by a study participant) of IMP or Alexion AxMP for medicinal purposes outside of the authorized product information, or for unauthorized IMPs or Alexion AxMPs, outside the intended use as specified in the protocol, including deliberate administration of the product by the wrong route.

Events of drug misuse, with or without associated AEs, are to be captured and forwarded to Alexion GPS via email or facsimile ([contact] or [name]) using the Alexion Clinical Study Drug Misuse or Drug Abuse Report Form. This form should be used both if the drug misuse happened in a study participant or if the drug misuse involves a person not enrolled in the study (such as a relative of the study participant).

Examples of drug misuse include but are not limited to:

- The drug is used with the intention to cause an effect in another person
- The drug is sold to other people for recreational purposes
- The drug is used to facilitate assault in another person
- The drug is deliberately administered by the wrong route
- The drug is split in half because it is easier to swallow, when it is stated in the
 protocol that it must be swallowed whole
- Only half the dose is taken because the study participant feels that he/she is feeling better when not taking the whole dose
- Someone who is not enrolled in the study intentionally takes the drug

10.5. Contraceptive Guidance and Collection of Pregnancy Information

10.5.1. Definitions

Woman of Childbearing Potential (WOCBP)

A woman is considered fertile following menarche and until becoming postmenopausal unless permanently sterile (see below).

If fertility is unclear (eg, amenorrhea in adolescents or athletes) and a menstrual cycle cannot be confirmed before first dose of study intervention, additional evaluation should be considered.

Women in the Following Categories Are Not Considered WOCBP

- Premenarchal
- Premenopausal female with one of the following:
 - Documented hysterectomy
 - Documented bilateral tubal ligation or bilateral salpingectomy
 - Documented bilateral oophorectomy

For individuals with permanent infertility due to an alternate medical cause other than the above, (eg, Mullerian agenesis, androgen insensitivity), Investigator discretion should be applied to determining study entry.

Note: Documentation can come from the site personnel's review of the participant's medical records, medical examination, or medical history interview.

- Postmenopausal female
 - A postmenopausal state is defined as no menses for 12 months without an alternative medical cause prior to the Day 1 Visit.
 - A high FSH level in the postmenopausal range may be used to confirm a
 postmenopausal state in women not using hormonal contraception or HRT.
 However, in the absence of 12 months of amenorrhea, confirmation with more
 than one FSH measurement may be required. In the absence of 12 months of
 amenorrhea the reason for not obtaining FSH levels should be documented by the
 Investigator at the time of Screening.
 - Females on HRT and whose menopausal status is in doubt will be required to use one
 of the non-estrogen hormonal highly effective or acceptable contraception methods if
 they wish to continue their HRT during the study. Otherwise, they must discontinue
 HRT to allow confirmation of postmenopausal status before study enrollment.
- Permanent sterilization at least 6 weeks prior to the Day 1 Visit.

10.5.2. Contraception Guidance

Contraceptive use by male or female participants should be consistent with local regulations regarding the methods of contraception utilized for those participating in clinical studies. If teratogenic effects are suspected to be transferred to a fetus/embryo from a female spouse/partner

of a male participant, pregnancy follow-up information will be obtained for the partner who becomes pregnant (refer to Section 10.5.3.1). In these cases, follow-up will be conducted on the pregnant partner in the same manner as a female participant who becomes pregnant during the study.

10.5.2.1. Guidance for Female Participants

Female participants of childbearing potential must have a negative serum pregnancy test as required by local regulations at Screening and a negative urine pregnancy test before the first dose of study intervention on Day 1. Additional requirements for pregnancy testing during and after dosing with study intervention are indicated in the SoA (Section 1.3).

The Investigator is responsible for the review of medical history, menstrual history, and recent sexual activity to decrease the risk for inclusion of a woman with an early undetected pregnancy.

The Investigator should evaluate the potential for contraceptive method in relationship to the first dose of study intervention.

Female participants of childbearing potential must use a highly effective or acceptable methods of contraception, including at least 1 of the following until at least 30 days after the final dose of study intervention. Highly effective methods are:

- Intrauterine device in place for at least 6 weeks prior to first dose of study intervention.
- Progestogen-only hormonal contraception associated with inhibition of ovulation (either oral, injectable, or implantable) for at least 6 weeks prior to first dose of study intervention.
- Intrauterine progestogen releasing system for at least 6 weeks prior to first dose of study intervention.
- Bilateral tubal occlusion for at least 6 weeks prior to first dose of study intervention.
- Combined (estrogen- and progestogen-containing) hormonal contraception (either oral, intravaginal, or transdermal) for at least 6 weeks prior to first dose of study intervention.
- 6. Surgical sterilization of the male partner (medical assessment of azoospermia is required if vasectomy was performed within the prior 6 months prior to the first dose of study intervention). Male partner is still required to use condom during sexual intercourse.
- Sexual abstinence for female participants:
 - Sexual abstinence is considered a highly effective method only if defined as
 refraining from heterosexual intercourse. In this study, abstinence is only acceptable
 if consistent with the participant's preferred and usual lifestyle. Abstinent female
 participants must refrain from heterosexual intercourse for at least 30 days after the
 final dose of study intervention.

Female participants of childbearing potential may also use the following acceptable methods (considered effective, but not highly effective means failure rate of \geq 1% per year) of contraception:

 Progestogen-only oral hormonal contraception where inhibition of ovulation is not the primary mode of action

- Male or female condom with or without spermicide
- Cervical cap, diaphragm, or sponge with spermicide
- 4. A combination of male condom with either cervical cap, diaphragm, or sponge with spermicide (double-barrier methods). If locally required, in accordance with Clinical Trial Facilitation Group (CTFG) guidelines, acceptable contraceptive methods are limited to those which inhibit ovulation as the primary mode of action.

The following methods of contraception are considered unacceptable (not allowed) in this study:

- Periodic abstinence (calendar, symptothermal, or post ovulation methods)
- Withdrawal (coitus interruptus)
- Spermicides only
- Lactational amenorrhea method
- Female condom and male condom should not be used together.

10.5.2.2. Guidance for Male Participants

Contraception is the responsibility of the heterosexually active male participants in the study, regardless of his female partner's method of contraception.

Male participants who have had a vasectomy > 6 months prior to the first dose of study intervention must use a condom during heterosexual intercourse. Male participants who have had a vasectomy < 6 months prior to the first dose of study intervention and those who have not had a vasectomy must use a condom (with or without spermicide) during heterosexual intercourse for at least 90 days (ie, 1 spermatogenesis cycle) after their final dose of study intervention.

10.5.2.2.1. Sexual Abstinence for Male Participants

Sexual abstinence is considered a highly effective method only if defined as refraining from heterosexual intercourse. In this study, abstinence is only acceptable if consistent with the participant's preferred and usual lifestyle. Abstinent male participants who become heterosexually active must use a condom with or without spermicide during intercourse.

Periodic abstinence (eg, calendar, symptothermal, or post ovulation methods for a female partner) is not considered a highly effective or acceptable method of contraception for male participants.

10.5.3. Collection of Pregnancy Information

Pregnancy data will be collected during this study for all female participants and female spouses/partners of male participants from the first dose of study intervention until the Safety Follow-up Visit. Any female participant who becomes pregnant during the study will be discontinued from the study intervention and withdrawn from the study. Exposure during pregnancy (also referred to as exposure in utero) can be the result of either maternal exposure or transmission of study intervention via semen following paternal exposure. If a female participant or a male participant's female spouse/partner becomes pregnant during the conduct of this study, the Investigator must submit the "Pregnancy/Breastfeeding Reporting and Outcome Form" to

Alexion GPS via facsimile or email. When the outcome of the pregnancy becomes known, the form should be updated and submitted to Alexion GPS. If additional follow-up is required, the Investigator will be requested to provide the information.

Exposure of an infant to study intervention during breastfeeding must also be reported (via the "Pregnancy/Breastfeeding Reporting and Outcome Form") and any AEs experienced by the infant must be reported to Alexion GPS via email or facsimile.

Pregnancy is not regarded as an AE unless there is a suspicion that the study intervention may have interfered with the effectiveness of a contraceptive medication. However, complications of pregnancy and abnormal outcomes of pregnancy are AEs and may meet the criteria for an SAE (eg, ectopic pregnancy, spontaneous abortion, intrauterine fetal demise, neonatal death, or congenital anomaly). Elective abortions without complications should not be reported as AEs.

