Period	Adhoc visit ^a		Open-label Extension Period							Safety Follow-up Period	Notes	
Week	After W50	W63	W76	W89	W102	W115	W128	W141	W154/ EDb	Evaluation for Renal Flare,	4 weeks post last dose	Unscheduled visits can be performed as needed. An ED Visit is required if participant
Days and Window		D442 ± 14	D533 ± 14	D624 ± 14	D715 ±14	D806 ±14	D897 ± 14	D988 ±14	D1079 ±14	Extrarenal SLE Flare, and Suboptimal Response Assessment Visit (LN only) ^c	30 (± 3) days post last dose	discontinues study early
Urinalysis and urine sediment		X	X	X	X	X	X	X	X	X		Section 8.2.4.3 and Section 10.2.
Participant safety card review		X	X	X	X	X	X	X	X	X		Confirm participants carry safety card at all times (Section 8.2.7).
Study Intervention•												
Study intervention compliance and accountability		Х	Х	Х	X	Х	Х	X	X			Participants on study intervention should bring all unused study intervention at each clinic visit for tablet counting.
Study intervention dispensing	c IN	х	х	х	х	X	х	х		120 11		Participants on study intervention will be provided with sufficient study intervention to last until their next study visit (except at W154 and ED).

^a Adhoc visit is only applicable for LN patients who are receiving hydroxychloroquine: When patients are switched from 120 mg to 180 mg after Week 50, or when placebo patients who are on allowed concomitant therapy initiate ALXN2050 at any dose due to a Renal Flare, additional ECG needs to be obtained at an adhoc visit 2 weeks (± 7 days) after the dose initiation or dose escalation.

^b For participants who discontinue study intervention prior to the end of the Open-label Extension Period, the ED Visit should be performed as soon as possible and a Safety Follow-up Visit should be performed 30 days after the last dose of study intervention.

Table 5: Schedule of Activities During the Open-label Extension Period and Safety Follow-up Period (Both LN and IgAN Cohorts)

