7. DISCONTINUATION OF STUDY INTERVENTION AND PARTICIPANT DISCONTINUATION/WITHDRAWAL

7.1. Discontinuation of Study Intervention

Participants must be considered for discontinuation from study intervention if any of the following occur during the study:

- Severe hypersensitivity reaction.
- Severe uncontrolled infection.
- Development of seizures (Section 10.14).
- Use of disallowed medication (as defined in Section 6.5.2) to be considered on a case-by-case basis.
- Participants in the LN cohort receiving hydroxychloroquine will be withdrawn if a QT/QTc interval > 500 msec or an increase > 60 msec from baseline occurs and is confirmed on recheck.
- Pregnancy or planned pregnancy. Any female participant who becomes pregnant
 while participating in the study will discontinue study intervention and will be
 withdrawn from the study.
- Alexion or the Investigator deems it is necessary for the participant.
- Adverse event that would, in the opinion of the Investigator, make continued treatment with study intervention an unacceptable risk.
- Participants in the LN cohort who have 2 Treatment Failures.

Data to be collected at the time of study intervention discontinuation and follow-up and for any further evaluations that need to be completed are provided in the SoA (Section 1.3).

The reason for discontinuation of study intervention will be recorded in the source documents and eCRF.

If the study intervention is definitively discontinued, every effort should be made to have the participant remain in the study and continue the study visits as per the SoA through Week 50 (Section 1.3).

Participants who discontinue study intervention and remain in the study may receive treatment consistent with local standard practice for their disease per Investigator judgment, as applicable.

 A Safety Follow-up Visit will be performed 30 days following the participant's last dose of study intervention.

If the participant does not agree to continue with the study visits after discontinuation of study intervention, the following activities should be completed:

- ED Visit should be performed as outlined in the SoA (Section 1.3).
- A Safety Follow-up Visit will be performed 30 days following the participant's last dose of study intervention

If a participant discontinues study intervention due to an AE, including SAEs, the event should be followed as described in Section 10.3.3.

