10.5.3.1. Male Participants with Partners Who Become Pregnant

- The Investigator will attempt to collect pregnancy information on any male participant's female partner who becomes pregnant while the male participant is in this study. This applies only to male participants who receive study intervention.
- After obtaining the necessary signed informed consent from the pregnant female partner directly, the Investigator will record pregnancy information on the appropriate "Pregnancy/Breastfeeding Reporting and Outcome Form" and submit it to Alexion within 24 hours of learning of the partner's pregnancy. The female partner will also be followed to determine the outcome of the pregnancy. Information on the status of the mother and child will be forwarded to Alexion. Generally, the follow-up will be no longer than 3 months following the delivery date. Any termination of the pregnancy will be reported regardless of fetal status (presence or absence of anomalies) or indication for the procedure.

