10.5.3.2. Female Participants Who Become Pregnant

- The Investigator will collect pregnancy information on any female participant who
 becomes pregnant while participating in this study. The initial information will be
 recorded on the appropriate form and submitted to Alexion within 24 hours of
 learning of a participant's pregnancy.
- For all Alexion products, both in development or postapproval, exposure during pregnancy must be recorded and the pregnancy followed, until the outcome of the pregnancy is known (ie, spontaneous miscarriage, elective termination, normal birth, or congenital abnormality), even if the participant discontinues the study intervention or withdraws from the study. The Investigator will collect follow-up information on the participant and the neonate and the information will be forwarded to Alexion. Generally, follow-up will not be required for longer than 3 months beyond the estimated delivery date. Any termination of pregnancy will be reported, regardless of fetal status (presence or absence of anomalies) or indication for the procedure.
- Pregnancy is not considered as an AE unless there is a suspicion that the study intervention may have interfered with the effectiveness of a contraceptive medication.
 While pregnancy itself is not considered to be an AE or SAE, any pregnancy

complication or elective termination of a pregnancy for medical reasons will be reported as an AE or SAE. A spontaneous abortion (occurring at < 22 weeks gestational age) or still birth (occurring at > 22 weeks gestational age) is always considered to be an SAE and will be reported as such. Any poststudy pregnancy-related SAE considered reasonably related to the study intervention by the Investigator will be reported to Alexion. While the Investigator is not obligated to actively seek this information in former study participants, he or she may learn of an SAE through spontaneous reporting.

[figure not shown]
 Any female participant who becomes pregnant while participating in the study will discontinue study intervention and be withdrawn from the study.

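### For men under the 90-day post-dose condom rule who leave the study at the Safety Follow-up Visit, planned partner-pregnancy collection stops at about day 30, leaving about 60 of those 90 days uncovered

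*Protocol*

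**What the plan says.** **Post-dose period for men.** Protocol 10.5.2.2 requires condom use "for at least 90 days (ie, 1 spermatogenesis cycle) after their final dose of study intervention". This applies to men without a vasectomy and to men whose vasectomy was less than 6 months before first dose. Men with an older vasectomy must also use a condom, but no post-dose duration is given for them.

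**Collection period.** Protocol 10.5.3 collects pregnancy data for female participants and for "female spouses/partners of male participants from the first dose of study intervention until the Safety Follow-up Visit". The partner-specific rule in 10.5.3.1 concerns any "female partner who becomes pregnant while the male participant is in this study".

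**Timing of the closing visit.** Protocol 7.1 states: "A Safety Follow-up Visit will be performed 30 days following the participant's last dose of study intervention". Table 5 of the Schedule of Activities gives the window as "30 (± 3) days post last dose" and lists no later contact.

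**Route of exposure.** Protocol 10.5.3 counts as exposure in utero both maternal exposure and "transmission of study intervention via semen following paternal exposure".

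**Other reporting routes.**
- Protocol 10.3.1 requires pregnancies during maternal or paternal exposure to be reported within 24 hours of the site becoming aware of them, and fetal outcome data to be collected.
- Protocol 10.5.3.2, under female participants, adds: "Any poststudy pregnancy-related SAE considered reasonably related to the study intervention by the Investigator will be reported to Alexion".
- Protocol 10.5.2 says that, if teratogenic effects are suspected, "pregnancy follow-up information will be obtained for the partner who becomes pregnant", and refers to 10.5.3.1.

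**The concern.** The protocol gives a biological reason for the 90 days, one spermatogenesis cycle, and names semen as a route by which a fetus could be exposed. One would expect collection of partner pregnancies to run as long as the precaution does. Instead, the cut-off for partners is the same as for female participants. For women this fits: 10.5.2.1 asks for contraception until at least 30 days after the final dose, and collection ends at about day 30. For men the precaution lasts three times as long as the collection, and no section explains the difference.

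What is at stake is the completeness of the pregnancy-exposure record. Table 6 lists pregnancy exposure among the risks and states that ALXN2050 has not been studied in pregnant women, so even a few partner pregnancies would carry information. An uncomplicated pregnancy is ordinarily not an adverse event under 10.5.3, so routine adverse-event reporting would not pick one up. The efficacy endpoints are not involved.

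**Working it through.** The plan states no figure for this coverage, so there is none to reproduce. The check sets the protocol's own periods side by side.

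**Inputs**
- Post-dose condom period for the men concerned: 90 days (10.5.2.2).
- End of planned collection: Safety Follow-up Visit (10.5.3), on day 30, window day 27 to day 33 (7.1; Table 5).
- Maximum treatment duration: 154 weeks (4.1).
- Week 50 Visit: Day 351 (Tables 3 and 4).

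**Uncovered part of the post-dose period**

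Uncovered days = 90 − day of the Safety Follow-up Visit.

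| Visit on day | Uncovered days | Share of 90 |
|---|---|---|
| 27 | 90 − 27 = 63 | 63/90 = 70.0% |
| 30 | 90 − 30 = 60 | 60/90 = 66.7% |
| 33 | 90 − 33 = 57 | 57/90 = 63.3% |

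**Against treatment plus the post-dose period, for a man who completes the study**

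154 × 7 + 90 = 1,168 days, and 60/1,168 = 5.1%. The gap is two thirds of the post-dose tail but about 5% of the whole span.

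**Women compared with men**

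| | Contraception after last dose | Planned collection after last dose |
|---|---|---|
| Female participants | at least 30 days (10.5.2.1) | about 30 days (10.5.3) |
| Men under the 90-day rule | at least 90 days (10.5.2.2) | about 30 days (10.5.3) |

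**Men who stop dosing early**

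Under 7.1, men who stop before Week 50 are encouraged to stay on visits through Week 50. They remain in the study, so 10.5.3.1 may cover them for longer than 10.5.3 does. On that reading, nominal cover to day 90 needs a last dose on or before Day 351 − 90 = Day 261. During the open-label extension, Table 5 gives early stoppers only an early discontinuation visit and the 30-day visit, so they are in the same position as men who complete the study.

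**Do the other routes close the gap?**
- 10.3.1 is triggered by awareness and has no stated end date, but it does not say how long paternal exposure lasts after the last dose and schedules no contact.
- The poststudy clause in 10.5.3.2 covers serious adverse events judged related, which the investigator is not obliged to seek.
- 10.5.2 depends on suspected teratogenicity and leads back to 10.5.3.1.

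None of these amounts to planned collection to day 90.

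**The case against.** The best counter-argument is that the protocol does not depend on 10.5.3 alone. 10.3.1 expressly names paternal exposure and sets no cut-off at the Safety Follow-up Visit. 10.5.3.2 says that, for all the sponsor's products, exposure during pregnancy is to be recorded and followed to outcome, even after withdrawal. That sentence sits under female participants, but 10.5.3 defines such exposure to include the semen route. A reader might infer that partner pregnancies after day 30 are bound to go unreported. The documents do not support that: they may be reported if the site hears of them. What remains is that no section ties this to the 90 days or plans to ask.

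Two further inferences also go too far.
- **Late recognition.** One might think that a pregnancy conceived during the study but recognised after day 30 is excluded. 10.5.3.1 turns on when the partner became pregnant and counts its 24 hours from when the site learns of it, so such a case is arguably covered.
- **Every man, whenever dosing stops.** Men with a vasectomy more than 6 months before first dose have no stated 90-day period. Men who stop early may stay in the study to Week 50. The SAP introduction says that study intervention was paused as of 06 Sep 2024, not that participants left the study. Men who received only placebo had no drug exposure to transmit.

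It is also fair that the consent form may tell participants to report later pregnancies. Consent pages are not available here, so the absence of such an instruction cannot be claimed.

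**Conclusion.** The mismatch stands in a limited form. For men under the 90-day rule who complete the study or leave it at the Safety Follow-up Visit, planned partner-pregnancy collection ends 60 days (57 to 63) short of the protocol's own post-dose period. A reader might describe this as two thirds of the exposure window. That overstates it: the treatment period is fully covered, the protocol describes the 90 days as a condom-use period, and the share of treatment plus post-dose time is about 5% for a man who completes 154 weeks.

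The conclusion assumes that participation ends at the Safety Follow-up Visit and that awareness-based reporting does not replace planned collection. It affects the completeness of safety data only. It is a worthwhile, inexpensive improvement and does not threaten the trial's conclusions.

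**What to change.** Reconcile Protocol 10.3.1, 10.5.2.2, 10.5.3 and 10.5.3.1 so that collection of partner pregnancies covers conceptions up to the end of the protocol's existing 90-day post-dose period for the men to whom it applies. State a single end point, so that 10.5.3 (the visit) and 10.5.3.1 (time in the study) no longer differ. At the Safety Follow-up Visit, remind these men to report any such pregnancy. Use the existing pregnancy form and outcome follow-up.

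A single telephone contact at or shortly after Day 90 is an optional way to do this. It could still miss a very recent conception, so the reminder is needed in any case.

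The cost is a few sentences at the next amendment and a small amount of site contact after the last visit. If the call were made a scheduled procedure, the end of study for these men could move by up to about 60 days. No change to the contraceptive duration is proposed.
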